2. Ease of use & convenience was somewhat better with tirbanibulin	n (%)
3. Ease of use & convenience was the same with tirbanibulin	n (%)
4. Ease of use & convenience was somewhat worse with tirbanibulin	n (%)
5. Ease of use & convenience was much worse with tirbanibulin	n (%)
(1 / 2) Ease of use & convenience was much / somewhat better with tirbanibulin	n (%)
(3) Ease of use & convenience was the same with tirbanibulin	n (%)
(4 / 5) Ease of use & convenience was somewhat / much worse with tirbanibulin	n (%)

RS5: Compared to your experience with your most recent topical treatment for AK (other than tirbanibulin (Klisyri®), how would you rate your overall satisfaction (considering the factors such as convenience/ ease of use, duration and severity of skin reactions, impact on daily life, etc.) with tirbanibulin (Klisyri®) treatment?

1. My satisfaction is much better with tirbanibulin	n (%)
2. My satisfaction is somewhat better with tirbanibulin	n (%)
3. My satisfaction is same with tirbanibulin	n (%)
4. My satisfaction is somewhat worse with tirbanibulin	n (%)
5. My satisfaction is much worse with tirbanibulin	n (%)

(1 / 2) My satisfaction is much / somewhat better with tirbanibulin	n (%)
(3) My satisfaction is same with tirbanibulin	n (%)
(4 / 5) My satisfaction is somewhat / much worse with tirbanibulin	n (%)

Note: Data from patient DCF, from week-24.

Table 1.32 Factors Influencing Overall Patient Satisfaction with Tirbanibulin, If Retreated with Tirbanibulin after Week 8

TT6_2 What factors influenced your response to the previous question (RS5) about your overall satisfaction with tirbanibulin (Klisyri®)? **Selected**

Domain	Week 24	Week 24
	If retreated with Klisyri® (N=x)	If retreated with another topical treatment (N=x)
[TT6_2r1] Product convenience: Length of treatment, frequency, and easiness to take, etc.	n (%)	n (%)
[TT6_2r2] Product effectiveness: Impact on skin appearance.	n (%)	n (%)
[TT6_2r3] Product effectiveness: Impact on AK lesion clearance.	n (%)	n (%)
[TT6_2r4] Product effectiveness: Amount of time it takes to start working.	n (%)	n (%)
[TT6_2r5] Product side-effects: Amount of time it takes for local skin reactions to resolve.	n (%)	n (%)
[TT6_2r6] Product side-effects: Number and type of local skin reactions.	n (%)	n (%)
[TT6_2r7] Product side-effects: Severity of the local skin reactions.	n (%)	n (%)
[TT6_2r8] Product tolerability: Ability to adhere to treatment dose, or intensity.	n (%)	n (%)
[TT6_2r9] Other:		
TT6_2r9oe	n (%)	n (%)

Note: Data from patient DCF, from week-24.

Table 1.33 Top-3 Factors Influencing Overall Patient Satisfaction with Tirbanibulin Ranking, If Retreated with Tirbanibulin after Week 8

TT6_2A Among the list of factors that influenced your overall satisfaction with tirbanibulin (Klisyri®), please identify the three most important factors and rank them on a scale of importance from 1 to 3, where 1 is the first most important factor, 2 is the second most important factor and 3 is the third most important factor to you, by entering a number in the boxes next to only those factors in the following list.

Domain	Rank 1	Rank 2	Rank 3	Average Rank
[TT6A_2r1] Product convenience: Length of treatment, frequency, and easiness to take, etc. (N=x)	n (%)	n (%)	n (%)	
[TT6A_2r2] Product effectiveness: Impact on skin appearance. (N=x)	n (%)	n (%)	n (%)	
[TT6A_2r3] Product effectiveness: Impact on AK lesion clearance. (N=x)	n (%)	n (%)	n (%)	
[TT6A_2r4] Product effectiveness: Amount of time it takes to start working. (N=x)	n (%)	n (%)	n (%)	
[TT6A_2r5] Product side-effects: Amount of time it takes for local skin reactions to resolve. (N=x)	n (%)	n (%)	n (%)	
[TT6A_2r6] Product side-effects: Number and type of local skin reactions. (N=x)	n (%)	n (%)	n (%)	
[TT6A_2r7] Product side-effects: Severity of the local skin reactions. (N=x)	n (%)	n (%)	n (%)	
[TT6A_2r8] Product tolerability: Ability to adhere to treatment dose, or intensity. (N=x)	n (%)	n (%)	n (%)	
[TT6A_2r9] Other: (N=x) TT6A_2r9oe	n (%)	n (%)	n (%)	

Note: Data from patient DCF, from week-24. Note: Data from patient DCF. Percentages are based on number of patients choosing a particular attribute to previous question (TT6_2).

Table 1.34 Top-3 Factors Influencing Overall Patient Satisfaction with Tirbanibulin Ranking, If Retreated with Another Topical Treatment after Week 8

TT6_2A Among the list of factors that influenced your overall satisfaction with tirbanibulin (Klisyri®), please identify the three most important factors and rank them on a scale of importance from 1 to 3, where 1 is the first most important factor, 2 is the second most important factor and 3 is the third most important factor to you, by entering a number in the boxes next to only those factors in the following list.

Domain	Rank 1	Rank 2	Rank 3	Average Rank
[TT6A_2r1] Product convenience: Length of treatment, frequency, and easiness to take, etc. (N=x)	n (%)	n (%)	n (%)	
[TT6A_2r2] Product effectiveness: Impact on skin appearance. (N=x)	n (%)	n (%)	n (%)	
[TT6A_2r3] Product effectiveness: Impact on AK lesion clearance. (N=x)	n (%)	n (%)	n (%)	
[TT6A_2r4] Product effectiveness: Amount of time it takes to start working. (N=x)	n (%)	n (%)	n (%)	
[TT6A_2r5] Product side-effects: Amount of time it takes for local skin reactions to resolve. (N=x)	n (%)	n (%)	n (%)	
[TT6A_2r6] Product side-effects: Number and type of local skin reactions. (N=x)	n (%)	n (%)	n (%)	
[TT6A_2r7] Product side-effects: Severity of the local skin reactions. (N=x)	n (%)	n (%)	n (%)	
[TT6A_2r8] Product tolerability: Ability to adhere to treatment dose, or intensity. (N=x)	n (%)	n (%)	n (%)	
[TT6A_2r9] Other: (N=x) TT6A_2r9oe	n (%)	n (%)	n (%)	

Note: Data from patient DCF, from week-24. Percentages are based on number of patients choosing a particular attribute to previous question (TT6_2).

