2 INTRODUCTION: BACKGROUND INFORMATION AND SCIENTIFIC RATIONALE

2.1 Background Information

Actinic Keratosis (AK) a common skin condition in which excessive and prolonged exposure to ultraviolet radiation. AK typically affects around 58 million people in the US and is more common in older adults, males, and those who are fair skinned. (Kempers et al, 2020). AK manifests as scaly, red lesions on face, trunk, scalp, and other sun exposed extremities; it could lead to epidermal lesions and eventually progress to squamous cell carcinomas (SCC) if left untreated (Khanna et al., 2017), with up to 65% of SCC arising from pre-existing AKs (Marks et al, 1988; Criscione et al, 2009). The rationale behind treating every AK lesion is based on the difficulty in predicting which single AK lesion will progress to SCC (Werner et al, 2015; Drake et al, 1995). The goal of treatment is to eliminate AK lesions, thereby minimizing their risk of progression to invasive SCC and reducing the associated morbidity and mortality, while obtaining the best cosmetic outcomes. While the clinical trials have compared the treatment outcomes of different therapies (Zane et al, 2016), patient reported outcomes (PROs), including patient preferences and what patients value the most for the AK treatment could improve total patient management in AK (Esmann et al, 2015, Siegel et al, 2017, Kopasker et al., 2019).

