6.1 Sample Size Considerations

No formal sample size and power calculations were undertaken. Considering the descriptive nature of the study and the feasibility of recruiting the study population, approximately 300 study Subjects from across a maximum of 50 clinical sites for the entire study has been identified as a sample to guide the planned analysis addressing the study objectives.

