6.3.3 Subgroup Analysis

Primary, secondary, and additional (non-safety) endpoints may be summarized and repeated for the following subgroups, if sample size permits, using FAS:

- Gender: male and female
- Age groups: ≤ 49 years, 50-64 years, and ≥ 65 years.
- Fitzpatrick skin type: I/II, and III/IV/V/VI.
- Skin photodamage at baseline: absent/mild, moderate/severe.
- History of skin cancer: yes and no.
- AK Treatment location: face only, scalp only, both face & scalp.
- Prior treatment experience, as applicable:
 - Cryosurgery vs. all others;
 - Other topical treatments vs. all others;
 - Treatment naïve vs. all others.

Subgroup analyses based on patient retreatment status between Week-8 and Week-24 visits (Klisyri vs. other topicals vs. non topicals vs. not retreated) may be considered for relevant outcome measures, based on data availability.

Subgroup analyses will either assess the difference in outcomes within a specific strata at a given time period (for measures collected only at Week-8 and/or Week-24), or assess CFB within a specific strata (for measures collected at baseline and at Week-8 and/or week-24).

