Subgroups	Symptoms			Emotions			Functioning		
	Baseline n, Mean	Wk-8 n, Mean	P	Baseline n, Mean	Wk-8 n, Mean	P	Baseline n, Mean	Wk-8 n, Mean	P
Gender									
Male									
Female									
Age Group									
≤ 49 years									
50 – 64 Years									
≥ 65 years									
AK Treatment Location									
Face									
Scalp									
Both									
BL Fitzpatrick Skin Type									
I / II									
III / IV / V / VI									
BL Skin Photodamage									
Absent/mild									
Moderate/Severe									
BL History of Skin Cancer									
Yes									
No									
Prior Treatment Experience: Use of Cryosurgery									
Yes									
No									
Prior Treatment Experience: Use of Other Topical Treatments									
Yes									
No									
Prior Treatment Experience: Treatment Naïve at Baseline									
Yes									
No									

P-values correspond to CFB at week-8, within respective strata.

Table 1.10 Patient Evaluation of Overall Appearance in the Original Treated Area

Questions	PER1 Week 8 (N=x)	PER24_1 Week 24 (N=x)
Compared to [8 or 24] weeks ago (at the beginning of the study), how has the overall appearance of the skin in the original AK treated area changed?	Mean (SD), Median, Min, Max	Mean (SD), Median, Min, Max
1. Much Worse	n (%)	n (%)
2. Somewhat Worse	n (%)	n (%)
3. No Change	n (%)	n (%)
4. Somewhat Improved	n (%)	n (%)
5. Much Improved	n (%)	n (%)
(1 / 2) Much / Somewhat Worse	n (%)	n (%)
(3) No Change	n (%)	n (%)
(4 / 5) Somewhat / Much Improved	n (%)	n (%)

Table 1.11 Subgroup Analysis of Patient Evaluation of Overall Appearance in the Original Treated Area

Subgroups	% Somewhat/Much Improved	Week 8 n (%)	Week 24 n (%)
Gender			
Male			
Female			
p -value			
Age Group			
≤ 49 years			
50 – 64 Years			
≥ 65 years			
p -value			
AK Treatment Location			
Face			
Scalp			
Both			
p -value			
Fitzpatrick Skin Type			
I / II			
III / IV / V / VI			
p -value			
Skin Photodamage			
Absent/mild			
Moderate/Severe			
p -value			
History of Skin Cancer			
Yes			
No			
p -value			
Prior Treatment Experience: Use of Cryosurgery			
Yes			
No			
p -value			
Prior Treatment Experience: Use of Other Topical Treatments			
Yes			
No			

p -value		
Prior Treatment Experience: Treatment Naïve at Baseline		
Yes		
No		

p-values correspond to difference between strata within respective time periods.

Table 1.12 Treatment Satisfaction Questionnaire for Medication (TSQM-9): Patient Scores in the Original Treated Area

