How do you rate the current severity of skin photodamage in the AK affected area?			
Responses will need to be recoded	AK4	AK8_3	AK8_3
0. Absent	n (%)	n (%)	n (%)
1. Mild	n (%)	n (%)	n (%)
2. Moderate	n (%)	n (%)	n (%)
3. Severe	n (%)	n (%)	n (%)
Absent/ Mild (0/1)	n (%)	n (%)	n (%)
Moderate/Severe (2/3)	n (%)	n (%)	n (%)
Who did the evaluation of patient's AK severity?			
1. Dermatologist	AK5	AK8_4	AK8_4
2. Nurse practitioner	n (%)	n (%)	n (%)
3. Physician's assistant	n (%)	n (%)	n (%)
How was the evaluation of AK severity done?			
1. During in-person patient visit (face-to-face)	AK6	AK8_5	AK8_5
2. Via tele-health visit (video)	n (%)	n (%)	n (%)

Table 2.8 CFB for Current Severity of Photodamage in the Original Treated Area

Domain	CFB in Proportion at Week 8 N=X (%)	p-value	CFB in Proportion at Week 24 N=X (%)	p-value
How do you rate the current severity of skin photodamage in the AK affected area?				
Absent (0)	%		%	
Mild / Moderate / Severe (1 / 2 / 3)	%	p	%	p
Absent / Mild (0 / 1)	%		%	
Moderate / Severe (2 / 3)	%	p	%	p

Table 2.9 Subgroup Analysis of Current Severity of Photodamage in the Original Treated Area

Subgroups	% Absent / Mild (0 / 1)		Baseline		Week 8		Week 24	
		n (%)		n (%)	P	n (%)	P	
Gender								
Male								
Female								
Age Group								
≤ 49 years								
50 – 64 Years								
≥ 65 years								
AK Treatment Location								
Face								
Scalp								
Both								
Fitzpatrick Skin Type								
I / II								
III / IV / V / VI								
Skin Photodamage								
Absent/mild								
Moderate/Severe								
History of Skin Cancer								
Yes								
No								
Prior Treatment Experience: Use of Cryosurgery								
Yes								
No								
Prior Treatment Experience: Use of Other Topical Treatments								
Yes								
No								
Prior Treatment Experience: Treatment Naïve at Baseline								
Yes								
No								

P-values correspond to CFB at respective time periods, within the corresponding strata.

Table 2.10 Clinician Evaluation of IGA in the Original Treated Area

Character	Week 8 (N=x)	Week 24 (N=X)
Overall, how is your patient's AK in the original treated area right now?		
Responses will need to be recoded	AK8_1	AK8_1
0. Completely Cleared	n (%)	n (%)
1. Partially Cleared	n (%)	n (%)
2. Moderately Cleared	n (%)	n (%)
3. Minimally Cleared	n (%)	n (%)
4. Not Cleared	n (%)	n (%)
(0 / 1) Completely/Partially Cleared	n (%)	n (%)
2 Moderately Cleared	n (%)	n (%)

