3 /4 Minimally/ Not Cleared	n (%)	n (%)

Table 2.11 IGA Success at Week 8 in the Original Treated Area

Character	Week 8
IGA Success	N=x
No	n (%)
Yes	n (%)

Note: IGA success at Week 8, defined as an IGA score of completely cleared (0) or partially cleared (1) in AK status in the original treated area at Week 8. The denominator for the percentages is the number of patients with available data (N=XX). X patients had missing data at Week 8.

Table 2.12 Subgroup Analysis of IGA Success

% IGA Success (Completely/Partially Cleared)		Week 8 n (%)	Week 24 n (%)
Subgroups			
Gender			
Male			
Female			
p -value			
Age Group			
≤ 49 years			
50 – 64 Years			
≥ 65 years			
p -value			
AK Treatment Location			
Face			
Scalp			
Both			
p -value			
Fitzpatrick Skin Type			
I / II			
III / IV / V / VI			
p -value			
Skin Photodamage			
Absent/mild			
Moderate/Severe			
p -value			
History of Skin Cancer			
Yes			
No			
p -value			
Prior Treatment Experience: Use of Cryosurgery			
Yes			
No			
p -value			
Prior Treatment Experience: Use of Other Topical Treatments			
Yes			
No			
p -value			

Prior Treatment Experience: Treatment Naïve at Baseline

Yes

No

p-value

P-values correspond to difference between strata within respective time periods.

Table 2.13 Clinician Evaluation of Overall Appearance in the Original Treated Area

Character	Week 8 (N=x)	Week 24 (N=X)
Compared to 8 / 24 weeks ago, how has the patient's overall appearance of the skin in the original AK treated area changed?		
1. Much Worse	AK8_2	AK8_2
2. Somewhat Worse	n (%)	n (%)
3. No Change	n (%)	n (%)
4. Somewhat improved	n (%)	n (%)
5. Much Improved	n (%)	n (%)
(1/2) Much/Somewhat Worse	n (%)	n (%)
(3) No Change	n (%)	n (%)
(4/5) Somewhat/Much Improved	n (%)	n (%)

Table 2.14 Subgroup Analysis of Clinician Evaluation of Overall Appearance in the Original Treated Area

% Somewhat / Much Improved	Week 8 n (%)	Week 24 n (%)
Subgroups		
Gender		
Male		
Female		
p -value		
Age Group		
≤ 49 years		
50 – 64 Years		
≥ 65 years		
p -value		
AK Treatment Location		
Face		
Scalp		
Both		
p -value		
Fitzpatrick Skin Type		
I / II		
III / IV / V / VI		
p -value		
Skin Photodamage		
Absent/mild		
Moderate/Severe		
p -value		
History of Skin Cancer		
Yes		
No		
p -value		
Prior Treatment Experience: Use of Cryosurgery		
Yes		
No		
p -value		
Prior Treatment Experience: Use of Other Topical Treatments		
Yes		
No		

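### The subgroup p-values for Skindex-16 and photodamage test each stratum's own change from baseline, so they cannot show whether outcomes differ between subgroups

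*SAP*

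**What the plan says.** SAP 6.3.3 sets two rules. Outcomes collected only after treatment are compared at a given visit. For outcomes that also have a baseline, subgroup analyses will "or assess CFB within a specific strata (for measures collected at baseline and at Week-8 and/or week-24".

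That wording is loose, but the table shells settle its meaning:

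- **Table 1.9 (Skindex-16 domain scores):** the P column has one cell per stratum and no factor-level row. Footnote: "P-values correspond to CFB at week-8, within respective strata".
- **Table 2.9 (photodamage, % absent/mild):** same layout, at Weeks 8 and 24. Footnote: "P-values correspond to CFB at respective time periods, within the corresponding strata".
- **Table 1.11 (patient-rated appearance):** one p-value row under a factor. Footnote: "p-values correspond to difference between strata within respective time periods".
- **Table 2.12 (IGA success):** same layout as Table 1.11. Footnote: "P-values correspond to difference between strata within respective time periods".

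The tables for looks, texture and relative satisfaction follow Tables 1.11 and 2.12. The TSQM subgroup tables (1.13 for patients, 2.16 for clinicians) follow Table 1.9, with a Baseline column and a within-strata change footnote, although SAP 5.2 schedules these questionnaires only at Weeks 8 and 24.

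**The concern.** A p-value for one stratum's own change answers whether that stratum moved. It does not answer whether men and women, or face and scalp, moved by different amounts. A significant result in one stratum beside a non-significant one in another is not evidence of a difference, and two significant strata can conceal one.

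Table 1.9 is the only subgroup table for the primary endpoint. It prints n and mean at each visit, but no mean change, SD, standard error or confidence interval. The p-value is therefore its only inferential figure, and readers are likely to compare strata by it. At stake is a mistaken claim that the treatment helps some kinds of patient and not others, or a real difference that goes unseen.

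**Working it through.** **Inputs.** SAP 6.1 gives "approximately 300 study Subjects from across a maximum of 50 clinical sites" and states "No formal sample size and power calculations were undertaken". The documents give no alpha, SD of change, effect size or stratum sizes, and name no test, so there is no figure of the plan's own to reproduce. Assumed here: two-sided 0.05, a paired t-test of change against zero, standardised change d of 0.2 to 0.5, and the splits below. Unequal strata are plausible, since protocol 2.1 says AK "is more common in older adults, males, and those who are fair skinned".

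**Count of p-values.** Strata per table: 2+3+3+2+2+2+2+2+2 = 20, from nine factors. Table 1.9 has 20 × 3 domains = 60 within-stratum p-values. Table 2.9 has 20 × 2 visits = 40.

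**Same true change everywhere.** The power of a stratum of size n is P(|T| > t(0.975, n−1)), with T noncentral t, n−1 degrees of freedom and noncentrality d√n. For two strata with powers π1 and π2, the chance that exactly one is significant is π1(1−π2) + π2(1−π1).

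- 270/30, d = 0.3: noncentralities 4.93 and 1.64, powers 0.998 and 0.355. Disagreement = 0.998 × 0.645 + 0.355 × 0.002 = 0.644.
- 150/150, d = 0.3: power 0.955 in each. Disagreement = 2 × 0.955 × 0.045, or 0.087 from unrounded powers.

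Chance of disagreement (%) when the true change is identical:

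| Split | d = 0.2 | d = 0.3 | d = 0.4 | d = 0.5 |
|---|---|---|---|---|
| 150/150 | 43.4 | 8.7 | 0.4 | 0.0 |
| 200/100 | 49.5 | 16.4 | 2.3 | 0.1 |
| 240/60 | 62.5 | 37.3 | 13.8 | 3.2 |
| 270/30 | 75.5 | 64.4 | 43.7 | 24.6 |

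For comparison, a two-sample test of change between strata, simulated 20,000 times at d = 0.3, was significant 5.1% of the time at 240/60 and 5.0% at 270/30.

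**Order reversed.** An observed d of 0.25 in 270 patients gives p = 0.00005. A larger d of 0.40 in 30 patients gives p = 0.037.

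**Real difference hidden.** Take mean changes of 10 points in 210 men and 5 in 90 women, SD 15 (all assumed).

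- Men: t = 10/(15/√210) = 9.66, p < 0.001.
- Women: t = 5/(15/√90) = 3.16, p = 0.002.
- Both improve, and the table stops there. The difference is 5 points with SE 15√(1/210 + 1/90) = 1.89, so the 95% CI is 5 ± 1.97 × 1.89 = 1.3 to 8.7.

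**Baseline photodamage in Table 2.9.** The outcome is % absent/mild, and one factor splits patients by absent/mild against moderate/severe at baseline. Those strata start at 100% and 0% by definition, so change can only go down in one and up in the other. Any contrast of change between them is an artefact.

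**The case against.** The strongest defence is that the study is descriptive. No objective asks whether outcomes differ by subgroup, 6.3.3 says only that subgroups may be summarised if numbers permit, and the footnotes label the test correctly. Whether a given stratum changed is a legitimate descriptive question. This stands as far as it goes: the tests are disclosed, not mislabelled. But a correct label does not make the p-value informative about subgroups, and the SAP itself uses the between-strata contrast for other endpoints.

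Table 1.9 also shows n and both visit means, so a reader can see stratum size and roughly subtract. That is true, but without an SD or interval the precision of the comparison cannot be judged. Protocol 12.3.4 assigns factors influencing outcomes to multivariate analyses, which could fill the gap, but the SAP has no matching section or table. The sample-size condition in 6.3.3 might remove the smallest strata, but it sets no threshold.

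Three stronger readings are tempting and not supported:

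- **That the p-values mostly reflect stratum size.** This holds only when changes are similar and strata unequal. At 150 per stratum they follow the effect: d = 0.1 gives p = 0.22 and d = 0.4 gives p < 0.0001.
- **That the primary endpoint gets the wrong test.** The point concerns its subgroup table only. The overall change is reported in Table 1.8.
- **That every satisfaction measure already has the between-strata contrast.** TSQM Tables 1.13 and 2.16 do not.

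One caution about the remedy also stands. On a 0–100 scale with a floor, unadjusted differences in change between strata partly reflect baseline differences, so they should be read as exploratory.

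**Conclusion.** The point holds for the subgroup tables. That within-stratum p-values cannot show a difference between strata needs no assumption. How misleading they would be does rest on assumptions: with an identical 0.3 SD change, disagreement on significance ranges from 9% at 150/150 to 64% at 270/30, and across changes of 0.2 to 0.5 SD from 43% to near zero and from 76% to 25% respectively. These figures are for a continuous score such as Skindex-16. The reasoning carries over to the photodamage proportions, but no figure was calculated for them. The change should be made, but nothing in the overall primary analysis depends on it.

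**What to change.** - **SAP 6.3.3:** replace the clause on outcomes with a baseline by a statement that change from baseline will be compared between the strata of each factor.
- **Table 1.9:** print n and mean (SD) change per stratum. For each factor and domain, print the between-strata difference in mean change with a 95% CI, with one overall test for the three-level factors. Label these exploratory and delete the 60 within-stratum p-values. That leaves 9 factors × 3 domains = 27 comparisons.
- **Table 2.9:** do the same with the difference in paired change, omitting the baseline-photodamage factor. That leaves 8 factors × 2 visits = 16 comparisons in place of 40 p-values.
- **Tables 1.13 and 2.16:** remove the Baseline column and the change-from-baseline p-values, and use the between-strata contrast at Week 8.

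The cost is SAP wording and four table shells, with no new data. Small strata will show wide intervals, which is a fair picture of what they can support.
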